**Radiographic Performance Requirements:**

Radiographic analysis of the tibial component employs 3 zones (Zone 1 – Zone 3) in the ML view and five zones (Zone 1 – Zone 5) in the AP view; analysis of the patellar component employs five zones (Zone 1 – Zone 5) in the Merchant view. Radiolucency in at least 50% of a zone and measuring at least 1 mm in width is defined as radiolucency present.

Subsidence is defined as settling of the prosthetic component in bone, and is related to the distance between fixed bony landmarks on the tibia and the prosthesis. It should be noted that Knee Society guidelines state that direct subsidence without angular movement cannot be detected because there is no reference point.

### **Surgical Details:**

Intraoperative data collected includes, but may not be limited to, the duration of surgery, tourniquet time, blood loss, units of blood transfused, anesthesia used, prophylaxis, surgical technique, surgical approach, soft tissues released, implanted prostheses and complications.

## **2.2 Safety**

All operative site events occurring at any time, as well as all serious adverse events (SAEs) occurring in the perioperative period (intraoperative to hospital discharge), are collected and compared to published data. It is expected that the AE rates reported for the Triathlon Tritanium Tibial Baseplate and Patella will be comparable to those reported in the literature for cemented primary total knee systems on the market. Details regarding AE definitions, recording and reporting are in Section 8 of this protocol, Adverse Events.

## **3 Clinical Study Plan**

### **3.1 Study Design**

A prospective, post-market, multi-center design is employed. Radiographs are assessed by an independent reviewer.

### **3.2 Number of Centers**

#### **3.2.1 Centers for Standard Data Collection**

Cases are to be enrolled at five to ten centers. The same center may be included in both arms. Conversely, a center may choose to participate in only a single arm. The enrollment goal is approximately 36 - 72 cases per center for Cohort 1 (cementless) and 15 - 30 cases per center for Cohort 2 (cemented) , and will vary dependent upon the number of participating centers. Although a goal is presented, there is no maximum limit to the number of cases that a center may enroll. In the event that a center far exceeds the enrollment goal, Stryker may ask the center to cease enrollment so as not to skew the data. All participating centers will comply with the federal regulations regarding patient informed consent and Institutional Review Board (IRB) or Ethics

CONFIDENTIAL

This material is the property of Stryker Orthopaedics. Do not disclose or use except as authorized in writing by Stryker.

Committee (EC) approval. Non-compliance of a study center may result in termination of the center's participation in the study.

### **3.3 Number of Subjects**

Cases are enrolled in the Cohort 1 (cementless) until a total of 356 cases receive the Triathlon Tritanium Tibial Baseplate, Triathlon Tritanium Patella, Triathlon CR or PS Beaded Femur with PA and the Triathlon Tibial Insert. All components in this cohort must be used in a cementless application. Enrollment in Cohort 2 (cemented) will begin upon completion of enrollment into the Cohort 1 (cementless), and will continue until a total of 144 cases receive the Triathlon Tibial Tray, Triathlon Patella, Triathlon CR or PS Femur and Triathlon Tibial Insert. All components in this cohort must be used in a cemented application.

### **3.4 Estimated Study Duration**

The enrollment period is estimated to be 24 months; cases for Cohort 1 (cementless) are evaluated as per the evaluation schedule until each case reaches 10 years. Cases for Cohort 2 (cemented) are evaluated as per the evaluation schedule until each case reaches 5 years. The total estimated study duration from enrollment to close-out activities is 12 years.

To allow for a learning curve with the use of the device, enrollment of cases into the study commences when three cases have been completed at the center using the Triathlon Tritanium Tibial Baseplate and Triathlon Tritanium Patella.

## **4 Eligibility**

The following criteria are used to distinguish patients eligible for enrollment into this study. Proper implant selection must consider design, fixation, and environmental variables including: patient weight, age, bone quality and size, activity level and preoperative level of health, as well as the surgeon's experience and familiarity with the device.

## **4.1 Inclusion Criteria**

1. Patient has signed an IRB/EC approved; study specific Informed Patient Consent Form.
2. Patient is a male or non-pregnant female age 18 – 75 years at time of study device implantation.
3. Patient has a diagnosis of Non-Inflammatory Degenerative Joint Disease (NIDJD).
4. Patient is a candidate for primary cementless total knee replacement, including a resurfaced patella.
5. Patient is willing and able to comply with postoperative scheduled clinical and radiographic evaluations and rehabilitation.

## **4.2 Exclusion Criteria**

1. Patient has a Body Mass Index (BMI) > 40.
2. Patient has a diagnosis of avascular necrosis or inflammatory arthritis.
3. Patient has an active or suspected latent infection in or about the affected knee joint at time of study device implantation.
4. Patient has a neuromuscular or neurosensory deficiency, which limits the ability to evaluate the safety and efficacy of the device.
5. Subject is diagnosed with a systemic disease (e.g. Lupus Erythematosus) or a metabolic disorder (e.g. Paget's Disease) leading to progressive bone deterioration.
6. Patient is immunologically suppressed or receiving steroids in excess of normal physiological requirements (e.g. > 30 days).
7. Patient is diagnosed with lumbar radicular pain.
8. Patient has a known sensitivity to device materials.
9. Patient is a prisoner.

# **5 Subject Enrollment**

## **5.1 Treatment Assignment**

All subjects in Cohort 1 (cementless) will receive the Triathlon Tritanium Tibial Baseplate, Triathlon Tritanium Patella, Triathlon CR or PS Beaded Femur with PA and the Triathlon Tibial Insert. All components in Cohort 1 (cementless) must be used in a cementless application.

CONFIDENTIAL

This material is the property of Stryker Orthopaedics. Do not disclose or use except as authorized in writing by Stryker.

All subjects in Cohort 2 (cemented) will receive the Triathlon Cemented Tibial Baseplate, Triathlon Cemented Patella, Triathlon CR or PS Cemented Femur and the Triathlon Tibial Insert. All components in Cohort 2 (cemented) must be used in a cemented application.

Patients will be enrolled until 356 subjects are implanted with the study device in Cohort 1 (cementless) and 144 subjects are implanted with the control device in Cohort 2 (cemented). Patients will not count toward enrollment unless they receive all components and use them as indicated per the protocol for the specified study cohort.

## **5.2 Randomization**

The study will enroll under a non-randomized concurrent control study design. Cohort 1 (cementless) and Cohort 2 (cemented) will be enrolled contemporaneously. In the event the same center participates in both arms a consecutive series of patients will be enrolled into Cohort 1 (cementless) until the enrollment objective is met before commencement of enrollment of patients into Cohort 2 (cemented).

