## Study Synopsis

Title	A prospective, post-market, multi-center study of the outcomes of the Triathlon Tritanium Knee System
Short Title	Triathlon Tritanium Knee Outcomes Study
Protocol Number	74
Phase	Post-market
Methodology	
This study is a prospective, non-randomized evaluation of the Triathlon Tritanium Knee System for primary total knee arthroplasty (TKA) with a cementless application in a consecutive series of patients who meet the eligibility criteria.
 
Cohort 1 (cementless): The first 356 cases enrolled will receive the Triathlon Tritanium Tibial Baseplate, Triathlon Tritanium Patella, Triathlon CR or PS Beaded Femur with PA and the Triathlon Tibial Insert. All components in this cohort must be used in a cementless application.
 
Cohort 2 (cemented): An additional 144 cases will receive the Triathlon Cemented Tibial Baseplate, Triathlon Cemented Patella, Triathlon CR or PS Cemented Femur and Triathlon Tibial Insert. All components in this cohort must be used in a cemented application.
 
The study uses literature control for the primary endpoint and a concurrent control (Cohort 2) for secondary endpoints.

Study Duration	
Approximate 12-year total duration
 

• Enrollment period of 24 months

• Follow-up of each primary Cohort 1 (cementless)TKA case to 10 years

• Follow-up of each primary Cohort 2 (cemented) TKA case to 5 years.

Study Center(s)	5-10 centers. The same center may be included in both arms. Conversely, a center may choose to participate in only a single arm.

CONFIDENTIAL

This material is the property of Stryker Orthopaedics. Do not disclose or use except as authorized in writing by Stryker.

Hypothesis	The success rate of the Triathlon Tritanium Knee, defined as absence of revision for aseptic loosening of the tibial baseplate at 2 years, is no worse than rates reported in the literature for cemented devices.

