#### **9.4.2 Sample Size Justification**

With a reference value of 99% for the success rate at 2 years, under the assumptions of 5% significance level (or 95% one-sided confidence interval), 95% power, 2% non-inferiority margin, the sample size is 267. After factoring a 15% lost to follow-up rate, the final sample size is 315 for the primary endpoint. An enrollment objective of 356 cases in Cohort 1 (cementless) was selected to power the primary objective of this study. In addition, 144 cases will be enrolled in Cohort 2 (cemented) to serve as a concurrent control for one of the secondary objectives.

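### Cohort 2 is called a concurrent control, but section 3.3 starts it only after Cohort 1 is full, and the 2-year score comparison it serves has no named method or committed adjustment

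*Combined protocol and SAP*

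**What the plan says.** On timing, section 5.2 describes a non-randomised design with a concurrent control and states that "Cohort 1 (cementless) and Cohort 2 (cemented) will be enrolled contemporaneously". The synopsis (Methodology) refers to "a concurrent control (Cohort 2) for secondary endpoints", its Reference Therapy row repeats the label, and section 9.4.2 says the 144 cemented cases are there "to serve as a concurrent control for one of the secondary objectives".

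Section 3.3 gives a different rule with no condition attached: "Enrollment in Cohort 2 (cemented) will begin upon completion of enrollment into the Cohort 1 (cementless". The synopsis fits that order. It says "The first 356 cases enrolled will receive the Triathlon Tritanium Tibial Baseplate", and describes the 144 cemented cases as additional. Section 5.2 then adds that a centre in both arms enrols consecutive patients into Cohort 1 "until the enrollment objective is met before commencement of enrollment of patients into Cohort 2 (cemented".

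On method, section 2.1.2 makes the between-cohort comparison of 2011 KSS, SF-12 and OKS at 2 years a secondary objective. The synopsis and section 9.1.4 leave its method to whatever statistical methods turn out to apply. Section 9.4.1 adds that scores will be compared and presented as improvement from the preoperative value, where that applies. Section 7.1 says preoperative data will describe the sample and serve to judge progress. No section names a model, a covariate or a centre term for this comparison.

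**The concern.** Sections 3.3 and 5.2 cannot both be followed. The plan claims a design property, concurrency, that its own enrolment rule does not deliver. This is the only controlled comparison made within the study, so the label matters for what the 2-year result can be said to show.

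If enrolment is sequential, anything that shifts between the two periods (case mix, surgical practice, rehabilitation) moves with the implant. If overlap comes only from different centres, centre differences move with the implant instead. Treatment is not randomised, so the cohorts may also differ at baseline. The raw 2-year score, the change from baseline and a baseline-adjusted score can then disagree, and the plan does not say which one counts.

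**Working it through.** **1. What each reading of the enrolment text allows.** Section 9.4.2 uses the term for the study total: "An enrollment objective of 356 cases in Cohort 1 (cementless) was selected to power the primary objective of this study". Section 3.2.1 uses a different word, goal, for the centre target.

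- If the objective in section 5.2 is the study total, two-arm centres cannot start Cohort 2 until all 356 cementless cases are in. Only cemented-only centres could overlap with Cohort 1.
- If it is the centre target, a centre that finishes early could enrol cemented cases while another is still enrolling cementless ones. Overlap is then only between different centres.
- Section 3.3 allows neither kind of overlap.

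**2. Timing under the section 3.3 order.** Inputs: 356 and 144 cases (synopsis), 24 months (section 3.4). Assumption: uniform accrual.

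- 24 months cover both cohorts: Cohort 1 fills at 24 × 356/500 = 17.1 months. Midpoints are 17.1/2 = 8.5 and (17.1 + 24)/2 = 20.5, a gap of 12.0 months. Overlap is zero.
- 24 months cover Cohort 1 only: Cohort 2 takes 144/(356/24) = 9.7 months and ends at month 33.7. Midpoints are 12.0 and 28.9, a gap of 16.9 months.

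**3. Centre goals.** Section 3.2.1 expects "approximately 36 - 72 cases per center for Cohort 1 (cementless) and 15 - 30 cases per center for Cohort 2 (cemented". Dividing by 10 and by 5 centres gives 356/10 = 35.6, 356/5 = 71.2, 144/10 = 14.4 and 144/5 = 28.8, which matches. Five cementless-only plus five cemented-only centres also give 71.2 and 28.8 per centre, within the same ranges and the limit of 10 centres. The goals do not show which layout was intended.

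**4. Can surgery date separate period from implant?** Assume 15% loss in both cohorts (section 9.4.2 states it for the primary endpoint): 0.85 × 356 = 302 and 0.85 × 144 = 122 evaluable. In SD units the SE is √(1/302 + 1/122) = 0.1073. Take a linear drift worth 0.1 SD between cohort means, no implant effect and a two-sided 5% test (the plan names none here).

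- Raw comparison: Φ(−1.96 + 0.1/0.1073) + Φ(−1.96 − 0.1/0.1073) = 15% false positives (15.9% by simulation).
- Adding surgery date: the share of date variance lying between cohorts is 0.712 × 0.288 × 12.0² ÷ (24²/12) = 29.5/48 = 0.615. The SE grows by 1/√(1 − 0.615) = 1.61, to 0.173. Simulation gives 0.172, with 4.7% false positives and bias near zero.

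A smooth common trend can therefore be removed, at a clear loss of precision. A step change at the switch cannot.

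**5. Why the choice of analysis matters (illustration only).** The documents give no SDs or correlations. Assume a baseline imbalance d = 0.3 SD, baseline-outcome correlation r = 0.3 to 0.5 and no true effect. The false-positive rate is Φ(−1.96 + |b|/s) + Φ(−1.96 − |b|/s). Here s is 0.1073 (raw), 0.1073√(2(1 − r)) (change) or 0.1073√(1 − r²) (adjusted).

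| Structure | Raw 2-year score | Change score | Baseline-adjusted |
|---|---|---|---|
| Both cohorts regress to a common mean | b = dr: 13–29% | b = d(r − 1): 29–38% | b = 0: 5% |
| Each regresses to its own mean | b = d: 80% | b = 0: 5% | b = d(1 − r): 37–54% |

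Under the common-mean structure the raw bias is +0.09 to +0.15 SD and the change-score bias −0.21 to −0.15 SD. The two results point in opposite directions.

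**6. Primary endpoint.** 0.99 × 0.01 × (1.645 + 1.645)²/0.02² = 267.85 (stated as 267), and 267/0.85 rounds up to the stated 315. Cohort 2 does not enter.

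**The case against.** The strongest defence is that section 5.2 describes the study as a whole, limits sequential enrolment to two-arm centres and leaves single-arm centres free to overlap. The synopsis gives an order of cases but never says when Cohort 2 begins. Both cohorts share one eligibility list (sections 4.1 and 4.2), which narrows case-mix differences. Sections 7.1 and 9.4.1 do look at baseline. The comparison is secondary, with no stated hypothesis, margin or alpha.

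Part of this stands. The direct conflict is between sections 3.3 and 5.2, with the synopsis as support, and baseline is not ignored. But section 3.3 makes no exception for single-arm centres. Overlap between different centres would exchange period confounding for centre confounding, and shared eligibility does not balance the cohorts.

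A reader might infer more than the documents support:

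- **That no model can undo the calendar effect.** As an absolute this is wrong. Surgery date varies within each cohort, so a smooth trend can be estimated (step 4).
- **That two-arm centres were the planning case.** The per-centre goals fit single-arm centres equally well (step 3).
- **That the baseline-adjusted model should outrank the change score in section 9.4.1.** The illustration gives worst cases of 37–54% and 29–38% respectively, so neither is shown to be better. The supportable request is to name the main one in advance.

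**Conclusion.** The conflict is real and sits in current text. Under section 3.3 the control is sequential: no overlap, and mean surgery dates about 12 months apart, or 16.9 if the 24 months cover Cohort 1 only. Both figures rest on uniform accrual. Under section 5.2, at most some overlap between different centres is possible. The 2-year between-cohort comparison has no committed method or adjustment.

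The false-positive rates show that the open choices can change the answer. Their inputs are assumed, so they do not estimate the likely error in this study. Nor should the point be read as a threat to the primary analysis, which section 9.1.3 tests against a literature-based rate. The consequence is limited to how the secondary comparison is labelled, analysed and interpreted, but that is worth settling before the 2-year data are seen.

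**What to change.** 1. Reconcile sections 3.3, 5.2 and 9.4.2 and the synopsis (Methodology and Reference Therapy). Say whether the enrolment objective in section 5.2 is the study total or the centre target. If the section 3.3 order stands, call Cohort 2 a sequential non-randomised control and report the difference as an association. State that period and implant can be separated only under an assumed smooth time trend, with lost precision, and not at all for a step change at the switch.
2. In the synopsis and section 9.1.4, replace the open-ended method with one pre-specified comparison using cohort, preoperative score, age, sex and BMI, accounting for centre. State whether the baseline-adjusted 2-year score or the section 9.4.1 change score is the main result. Give the other as a sensitivity analysis and explain that they rest on different assumptions. Add one sensitivity analysis with a surgery-date term and one restricted to centres contributing to both cohorts.
3. For KSS Expectation use neither the preoperative value nor a change score. The Appendix F forms ask beforehand what the patient expects and afterwards whether expectations were met, so the items are not the same measure.
4. State that adjustment removes measured imbalance only, and not centre confounding where centres are single-arm.

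The cost is protocol and SAP wording, one model and a few sensitivity analyses. Preoperative scores, date of birth, sex and BMI are already collected (sections 2.1.3 and 7.1, Appendix F). Enrolment need not change if the control is relabelled. The downside is a more modest claim and a little more analysis work.

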# **6 Device Description**

## **6.1 Study Device**

The Triathlon Tritanium Tibial Baseplate, Triathlon Tritanium Patella, Triathlon CR or PS Beaded Femur with PA and the Triathlon Tibial Inserts have been cleared for use in the United States; therefore, this study is considered a post-market assessment. All cases in Cohort 1 (cementless) must receive the Triathlon Tritanium Tibial Baseplate, Triathlon Tritanium Patella, Triathlon CR or PS Beaded Femur with PA and the Triathlon Tibial Insert.

The Triathlon Tritanium Tibial Baseplate features the Tritanium advanced fixation technology that closely resembles the porous structure of trabecular bone to promote biologic fixation. The Triathlon Tritanium Tibial Baseplate, the porous coating, solid keel, and solid pegs are built via Laser Rapid Manufacturing (LRM) with CP Titanium powder within a build envelope, and simultaneously bonded/melded onto a titanium alloy (Ti6Al4V ELI) substrate. CP Titanium powder is spread on top of the Ti6Al4V ELI substrate which is fixed to a piston inside the chamber. The laser beam is controlled and focused by computer to the powder bed. An argon

CONFIDENTIAL

This material is the property of Stryker Orthopaedics. Do not disclose or use except as authorized in writing by Stryker.

atmosphere is maintained within the chamber to prevent oxidation of the part during manufacturing.

The Triathlon Tritanium Tibial Baseplate is available in eight sizes and is coupled with the Triathlon Tritanium Patella which is available in five asymmetric sizes and four symmetric sizes. These components are coupled with the existing Triathlon CR or PS beaded femoral components and the N2VAC or X3 Triathlon Tibial Inserts. The combination of the Tritanium biologic fixation technology and the Triathlon Knee System design creates a two-tier high performance total knee system to provide surgeons with options for enhanced cementless knee fixation and joint stability which may meet the needs of today's younger and more active TKA patients. A description of the study device (Triathlon Tritanium Tibial Baseplate and Triathlon Tritanium Patella) follow. Appendix I provides a listing of all protocol-specified components. The catalog numbers for the study device are listed in Table 1 and Table 2.

**Triathlon Tritanium Tibial Baseplate:**

The catalog numbers for the Triathlon Tritanium Tibial Baseplate permissible according to this study protocol will be in the following format, where 'XXX' varies by size:

5536-B-XXX

**Triathlon Tritanium Patella:**

The catalog numbers for the Triathlon Tritanium Patella permissible according to this study protocol will be in the following format, where 'XXX' varies by size:

5552-L-XXX (asymmetric)

5556-L-XXX (symmetric)

Figure 1: Triathlon Tritanium Tibial Baseplate and Patella

Additionally, only the following **Stryker compatible** ancillary devices are to be used for Cohort 1 (cementless), according to this study protocol:

- Triathlon CR Beaded Femur with PA
- Triathlon PS Beaded Femur with PA
- Triathlon Tibial Inserts

The compatible Stryker components are listed in the surgical protocol.

For reference, a description of the compatible femoral components and tibial inserts follow. Appendix I provides a listing of all protocol-specified components. In the case of any uncertainty regarding device compatibility, the current version of the Triathlon Tritanium Knee System surgical protocol should be reviewed.

**Triathlon CR and PS beaded Femur:**

The catalog numbers for the Triathlon CR and PS beaded Femur permissible according to this study protocol will be in the following format, where 'XXX' varies by size:

5516-F-XXX (PS femur)

5517-F-XXX (CR femur)

### **Triathlon Tibial Inserts:**

The catalog numbers for the Triathlon Tibial Inserts permissible according to this study protocol will be in the following format, where 'XXX' varies by size:

5530-P-XXX (CR insert, conventional polyethylene)

5530-G-XXX (CR insert, X3)

5531-P-XXX (CS insert, conventional polyethylene)

5531-G-XXX (CS insert, X3)

5532-P-XXX (PS insert, conventional polyethylene)

5532-G-XXX (PS insert, X3)

